9.3. Multiplicity

There is only 1 primary endpoint and no interim analysis for efficacy will be performed. Therefore, the primary endpoint will be tested at the α =0.05 level (two-sided test).

9.4. Missing data

Patients that are lost to follow-up after the start of study drugs will be considered treatment failures in the mITT analysis.

9.5. Sample size calculation

In the pivotal trial on voriconazole and anidulafungin combination therapy the mortality in the voriconazole control group was 28% 6 weeks after the start of therapy. This study only included patients with an underlying haematological disease. Furthermore, in a large pragmatic trial with fewer exclusion criteria and in which a small number of ICU patients will be included as well, we expect a somewhat higher mortality of 35%, We consider a 33% lower overall mortality with combination therapy (=from 35% to 23,33%) compared to monotherapy of clinical importance. This leads to a sample size of 237 evaluable patients per group (=included in the mITT population as defined above) to show superiority of combination therapy compared with monotherapy with an alfa of 0.05 and a power of 80%. Follow-up for the primary endpoint is 6 weeks after the start of antifungal therapy.

9.6. Responsibility for data analysis

The coordinating investigator will be responsible for analyzing the study data.

9.7. Monitoring

This trial is part of the HOVON site evaluation visit program. Site evaluation visits will be performed for HOVON trials to review the quality of the site and not specifically the quality of a certain trial. It will enable HOVON to collect quality data and facilitate improvement of the participating sites. Data cleaning or monitoring of the performance of specific trials is not the goal of the site evaluation visits. Site evaluation visits will be performed according to the site evaluation visit plan.

The HOVON site evaluation visit plan applies to sites in the Netherlands and Belgium only. Monitoring of the quality of trial conduct in participating sites from other countries will be organized by the coordinating investigator or co-sponsor. The frequency and content of the site visits in other countries will be at least equal to the specifications of the site evaluation visit plan and are described in a monitoring plan provided by HOVON.

Direct access to source documentation (medical records) must be allowed for the purpose of verifying that the data recorded in the CRF are consistent with the original source data. The sponsor expects that during site visits the relevant investigational staff will be available, the source documentation will be available, and a suitable environment will be provided for review of study-related documents.

9.8. Interim efficacy analysis

An interim efficacy analysis will not be performed. One interim futility analysis will be performed after the inclusion of 50% of the planned sample (see 7.7).

10. COST-EFFECTIVENESS ANALYSIS

The cost-effectivity of combination therapy compared with triazole monotherapy will be analyzed only if a statistical difference (p0.05 or lower) is observed for the primary endpoint or for secondary endpoint 2. The full statistical analysis plan for endpoint 12 is therefore not yet complete but will be developed after the analysis of these endpoints has been completed and in collaboration with prof. dr. [name] of the institute of Medical Technology Assessment in Rotterdam (iMTA). The analysis will estimate if combination therapy is cost saving and if this is not the case the cost per quality adjusted life year of combination therapy compared to monotherapy will be calculated. For this, not only quality of life data, the (time to) death but also detailed data on each of the following clinical parameters that are associated with substantial increase in costs will be collected; Duration of hospital stay and number of days admitted to the intensive care unit, blood products and antifungal drugs administered as well as enteral or parenteral nutrition given between baseline and week 12 of follow-up. For the quality of life data collection, the EuroQOL EQ5D-5L questionnaire will be used (including the proxy or telephone version if needed, appendix 5). Because the majority of the patients with IA in our study will consist of patients treated for AML with intensive chemotherapy and of patients that received an allogeneic stem cell transplantation, previously published utility scores from these patient populations will be used to calculate the cost per quality adjusted life years gained (QALY) with combination therapy compared with monotherapy. 19 Apart from quality of life data, we will collect data on loss of income up to 24 weeks after inclusion to allow for an analysis of cost-effectivity from the society perspective. For this purpose, a set of dedicated questionnaires will be used (appendix 5).

The study population will consist of 3 major study populations: Patients receiving chemotherapy for AML, patients with graft-versus-host-disease and other patients. If a significant treatment effect of the intervention is observed in one of these subgroups, an exploratory cost-effectiveness analysis will be done for this subgroup.

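### The cost-effectiveness plan is to be written once by-arm mortality is known, and its rule gives cost per QALY only if combination does not appear cost saving, with no margin, interval or direction stated

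*Protocol*

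**What the plan says.** Section 10 of the protocol sets a condition for starting: cost-effectiveness "will be analyzed only if a statistical difference (p0.05 or lower) is observed for the primary endpoint or for secondary endpoint 2". It gives this condition as the reason for deferring the methods: "The full statistical analysis plan for endpoint 12 is therefore not yet complete", and the plan "will be developed after the analysis of these endpoints has been completed", together with an external health technology assessment institute.

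Inside the analysis it states a sequence: "The analysis will estimate if combination therapy is cost saving and if this is not the case the cost per quality adjusted life year" is calculated. It gives no test, interval or margin for a saving.

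Several elements are already fixed: a list of resource items, the instrument ("the EuroQOL EQ5D-5L questionnaire will be used"), a source of utilities ("previously published utility scores from these patient populations will be used to calculate the cost per quality adjusted life years gained"), and a trigger for exploratory analyses in the AML, GVHD and other groups. The periods differ. Resource use is described as ending at week 12 ("enteral or parenteral nutrition given between baseline and week 12 of follow-up"), while for productivity "we will collect data on loss of income up to 24 weeks after inclusion". The visit schedule in Appendix 2 registers hospital and ICU days to week 24.

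**The concern.** Leaving health-economic detail to a later document is normal. Here the protocol itself places that document after the comparative 6- and 12-week mortality results. The trial is open-label (section 3), has no data safety monitoring board (section 8.8), and its coordinating investigator is responsible for the analysis (section 9.6). Choices that move a cost-effectiveness result could then be made, even in good faith, with knowledge of which choice favours which conclusion.

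The sequence of cost saving first and cost per QALY otherwise adds a second problem. It treats the sign of an estimated mean cost difference as known, and that sign decides whether a cost-per-QALY result exists. Secondary objective 1 (section 2) asks about quality of life and cost-effectiveness and assigns both to endpoints 11 and 12. Endpoint 11 is time to hospital discharge (section 7.1.2), so the QALY question rests on endpoint 12 alone.

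**Working it through.** **1. What section 10 leaves unclear**
- Horizon: week 12 for resource items, week 24 for loss of income, and week 24 for hospital and ICU days in Appendix 2.
- Utilities: published scores are named for the cost-per-QALY calculation, and EQ-5D-5L data are collected as well. How the trial's own data enter is not stated.
- Perspective: income data allow a societal analysis, but no base case is named.

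**2. What the rule produces once the significance condition is met**
- Better survival, dearer: cost per QALY calculated.
- Better survival, cheaper: none calculated. This is conventional if the saving is clear.
- Worse survival, dearer: a ratio calculated, though it carries no useful information.
- Worse survival, cheaper: none calculated, although this trade-off most needs one.

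The last case can arise because the condition asks only for a statistical difference and the test is two-sided (section 9.3).

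**3. The plan's own figure, used here only as n**

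Inputs from section 9.5: mortality 35% v 23.33%, alpha 0.05, power 80%. Pooled variance, no continuity correction:

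n = [1.960 x sqrt(2 x 0.29165 x 0.70835) + 0.842 x sqrt(0.35 x 0.65 + 0.2333 x 0.7667)]^2 / 0.1167^2 = (1.260 + 0.537)^2 / 0.01362 = 237 per group, as stated.

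**4. How often the sign of the cost difference is wrong**

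SE = SD x sqrt(2/237) = 0.092 x SD. For a true difference D, P(wrong sign) = Phi(-|D|/SE).

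| True difference | P(wrong branch) |
|---|---|
| 0.5 SE | 31% |
| 1 SE | 16% |
| 2 SE | 2% |

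At D = 0 the branch is a coin toss. The consequence is one-sided: a result is lost only when a truly dearer combination looks cheaper.

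In money, on assumptions only (no cost SD or cost difference is in the documents), with a true extra cost of EUR 2,000:

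| Assumed SD (EUR) | SE (EUR) | P(appears cost saving) |
|---|---|---|
| 15,000 | 1,378 | 7% |
| 20,000 | 1,837 | 14% |
| 40,000 | 3,675 | 29% |
| 60,000 | 5,512 | 36% |

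None of these figures is conditioned on the significance condition being met.

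**5. How often the significance condition is met**

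Simulation of 200,000 trials with 237 per arm, unadjusted tests at 6 and 12 weeks:
- No effect, 12-week mortality assumed 5 to 15 points above 35%: met in about 7-8% of trials. By symmetry, half of these, about 4% of trials, favour monotherapy.
- Design effect, 12-week mortality assumed 45-47% v 33%: met in about 85-90%.

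**The case against.** The strongest defence has four parts.

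- The significance condition comes first, so no cost-per-QALY result is lost to cost noise unless a mortality difference has been declared. This stands, and it is why the percentages above are illustrations. But a condition on whether to run an analysis is no reason to delay choosing its method.
- When a treatment is both better and cheaper, leaving out the ratio is ordinary practice. This also stands. What remains is that the protocol would decide this from a point estimate, behind a condition with no direction.
- Uncertainty methods are usually left to a health-economic plan. A reader might infer that any saving would be reported without its uncertainty. The protocol does not say so: it is silent on uncertainty and calls the plan incomplete.
- A reader might infer that the cost-saving sequence is the only thing fixed, or might multiply two utility sources, two horizons and two perspectives into eight competing analyses. Section 10 supports neither. It also fixes the significance condition, the resource items, the questionnaire, the published utilities and the subgroup trigger. The utility source is named, and two perspectives can both be reported.

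None of this answers the timing. Section 10 states that the plan follows the results, so an analysis plan not shown here cannot be presumed to have settled it.

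**Conclusion.** The point holds for timing and for the decision rule. Section 10 schedules the endpoint 12 plan after the by-arm mortality results, with horizon, role of the trial's EQ-5D-5L data and base-case perspective unclear. It also withholds cost per QALY on an undefined finding of cost saving, whichever arm has the better survival.

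The size cannot be fixed from the documents. On a scale-free basis the branch is reliable only when the true cost difference is about 2 SE or more. It would go too far to say that the branch will be materially noisy in this trial, because that needs a cost SD and a cost difference that the protocol does not give. The cheaper-but-worse case is possible but uncommon: even with no true effect, a significant difference against combination arises in about 4% of trials, under the mortality assumptions above.

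This concerns a secondary endpoint. The primary mortality analysis and the data collection are unaffected, and quality-of-life data are collected in any case.

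**What to change.** - Sign off the endpoint 12 plan before any by-arm mortality analysis, which includes the interim futility analysis in section 7.7. It should fix the population, horizon, perspective, utility source (with the role of the trial's EQ-5D-5L data) and unit costs. The wording in section 10 that places the plan after the results should be replaced.
- The significance condition may stay.
- Replace the two-step sequence. Whenever the analysis is run, estimate incremental cost and incremental QALYs jointly with their uncertainty, for example with bootstrap intervals and net monetary benefit, whatever the sign of the cost difference and the direction of the survival difference.
- Reconcile the week 12 and week 24 periods between section 10 and Appendix 2.

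Cost: health-economic planning is brought forward and may go unused if the significance condition is not met. No new data are required.

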7.2. Randomisation, blinding and treatment allocation

This is a phase 3 non-blinded non-placebo controlled pragmatic trial. Randomization will be stratified according to the following 3 risk groups: Acute myeloid leukemia, graft-versus host disease and other.

Randomization and concealed allocation will be performed and guaranteed via randomization using blocks of different length and with the use of a randomization module

in the eCRF (Alea). Subjects will be randomized to a 1:1 allocation into 2 treatment group: monotherapy versus combination therapy.

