9. STATISTICAL ANALYSIS

9.1. Primary endpoint analysis

The primary endpoint is defined as all-cause mortality at 42 days (6 weeks) after randomization. The MITT population is considered the main analysis population.

The relation between randomly allocated treatment and the incidence of the primary endpoint in the MITT population will be described by

- the total number of endpoint events by allocated treatment;
 - a crude, unadjusted odds ratio. Logistic regression analysis will be conducted, with randomly allocated treatment as independent predictor variable and the incidence of the primary endpoint as dependent outcome variable;
 - an adjusted odds ratio. A multivariable logistic regression analysis will be applied. The effect of randomly allocated treatment will be adjusted for age, pulmonary or (also) extrapulmonary disease, ICU admission, baseline serum galactomannan status, post allogeneic stem cell transplantation status, and acute or chronic GVHD for which patients are receiving systemic immunosuppressive therapy.

The adjusted odds ratio will be considered the key primary endpoint analysis

The same analysis will be performed for secondary endpoints 2 to 6. The listed sub-populations will be analyzed using simple and multivariable logistic regression (the adjustment factors - as far as applicable - are listed above). Since these analyses will be considered exploratory only and these endpoints are defined as secondary endpoints, no correction for multiple testing will be performed.

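### Section 10 chooses which patient groups get a cost-effectiveness result by significance within the group, so a uniform effect would usually be reported for some strata only, and with an exaggerated gain

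*Protocol*

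**What the plan says.** Section 10 of the protocol contains two conditions. The first governs the whole-trial analysis: cost-effectiveness "will be analyzed only if a statistical difference (p0.05 or lower) is observed for the primary endpoint or for secondary endpoint 2", that is, 6-week or 12-week overall survival in the MITT population. The second closes the section. It first describes the groups: "The study population will consist of 3 major study populations: Patients receiving chemotherapy for AML, patients with graft-versus-host-disease and other patients". It then gives the rule: "If a significant treatment effect of the intervention is observed in one of these subgroups, an exploratory cost-effectiveness analysis will be done for this subgroup".

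These groups correspond to the randomisation strata in section 7.2: "Randomization will be stratified according to the following 3 risk groups: Acute myeloid leukemia, graft-versus host disease and other".

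For the test within a group, section 10 names no endpoint, significance level, direction, multiplicity correction or interaction test. It does not say whether the whole-trial condition must be met first, or which estimate of the survival gain enters the group's cost per QALY.

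The multiplicity statements elsewhere do not cover these tests. Section 9.3 concerns the primary endpoint: "There is only 1 primary endpoint and no interim analysis for efficacy will be performed". The statement in section 9.1 that "no correction for multiple testing will be performed" refers to secondary endpoints 2 to 6. The AML/GVHD/other split is not one of those; endpoints 5 and 6 divide non-ICU patients by haematological disease.

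**The concern.** A significant effect in one group and a non-significant effect in another is not evidence that the effect differs between them. In a trial sized for its overall comparison, each third or so of the patients has low power, so which groups reach significance is largely chance. Two consequences follow.

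First, a treatment that works equally in everyone would usually produce an economic result for some groups and none for others.

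Second, a small group reaches significance only when its observed gain is large, so the gain in a selected group is on average too big. If that same gain is used in the group's cost per QALY, combination therapy will look better value than it is. The protocol plans this work with a technology-assessment institute, so the figure may well be used.

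**Working it through.** **Inputs from the protocol.** Mortality 35% and 23.33%, 237 evaluable patients per arm, 80% power (section 9.5); two-sided 5% level for the primary endpoint (section 9.3); 1:1 allocation and three strata (section 7.2).

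**Assumptions.** The same 5% two-sided level for each group; one test per group, on 6-week mortality; 35% control mortality in every group. The protocol gives no group sizes, so shares of thirds, 50/25/25, 50/20/30, 40/20/40 and 40/15/45 were tried.

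**Step 1. The protocol's own figure.** With mean mortality 0.2917,

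n = [1.96·√(2·0.2917·0.7083) + 0.8416·√(0.35·0.65 + 0.2333·0.7667)]² / 0.1167² = (1.260 + 0.536)² / 0.01362 ≈ 237 per arm.

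The planned sample size is reproduced.

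**Step 2. Why a selected group exaggerates.** With 79 per arm (thirds), the observed difference must exceed about 1.96·√(2·0.2917·0.7083/79) = 14.2 points to be significant. That threshold already lies above the true 11.7. Power is Φ[(0.1167 − 0.1417)/√(0.4064/79)] = Φ(−0.35) ≈ 36%.

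**Step 3. Uniform planned effect, simulated** (400,000 trials per scenario, pooled two-proportion z-test):

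| Patients per arm in group | Power | Mean observed gain when significant | Ratio to true 11.7 |
|---|---|---|---|
| 36 | 20% | 26.6 points | 2.3 |
| 47 | 24% | 23.7 | 2.0 |
| 59 | 29% | 21.4 | 1.8 |
| 79 | 37% | 19.0 | 1.6 |
| 95 | 43% | 17.7 | 1.5 |
| 118 | 51% | 16.3 | 1.4 |

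Averaged over all selected groups, the mean gain is 19.0 points under each set of shares.

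For thirds, the chance that all three groups are selected is 0.367³ = 0.05 and that none is 0.633³ = 0.25. Some but not all are therefore selected in 1 − 0.05 − 0.25 = 0.70 of trials. The other shares give 70 to 71%, with all three selected in 4 to 5%.

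**Step 4. The same, keeping only trials with a significant overall 6-week result.** The mean selected gain is 19.1 points. Some but not all groups are selected in about 80 to 83% of these trials, and all three in 5 to 6%.

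**Step 5. A smaller uniform effect.** With a 20% relative reduction (35% to 28%, 7 points), a selected group shows about 18 points, or 2.6 times the truth.

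**Step 6. No effect.**
- Overall condition not applied to groups: at least one significant group in either direction, 1 − 0.95³ = 14.3% (simulated 14 to 15%); a significant benefit, 1 − 0.975³ = 7.3% (simulated 7.2 to 7.6%).
- Overall condition applied, 6-week endpoint only: about 3.2% in either direction, 1.6% for benefit.
- Overall condition applied, 6-week or 12-week endpoint (assuming 15% of 6-week survivors die by week 12): about 3.9% and 2.0%.

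**Step 7. Illustration for cost per QALY.** If the extra cost is held fixed and the QALY gain is proportional to the mortality difference, using 19.0 in place of 11.7 gives 11.7/19.0 = 0.62 of the true cost per QALY. Both conditions are simplifications.

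**The case against.** The strongest reply is that section 10 labels the group analysis exploratory, that the full plan for endpoint 12 is openly deferred, and that nothing here touches the primary analysis or the main economic analysis. On that view, the significance level, endpoint, correction and effect estimate are details for a later document. This largely stands for those details, and their absence is not the point. But the rule that selects a group is already written in the protocol, and the exploratory label limits the claim without correcting the selected estimate.

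A second reply is that the opening condition of section 10 may be meant to cover the groups too. That is a fair reading. A reader might infer that the rule lets a group result through after a null trial, in about 15% of null trials. The text does not support that: it is silent on whether the overall condition applies, and the 15% includes groups significant for harm, which cannot rest on an exaggerated survival gain. For a false benefit the rate is about 7.5% at most on one endpoint, and about 2% if the condition applies.

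It is also fair that describing the tests as uncorrected, and assuming that the group's own gain enters its cost per QALY, are inferences. The second is the natural reading, but it is not stated. The magnitudes depend on assumed group sizes and a common control mortality.

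**Conclusion.** The point holds as a flaw in the selection rule. Under the planned effect, identical in all strata, the rule would single out some but not all strata in about 70% of trials. It would attach to them a mean observed gain of about 19 points (about 16 to 27 by stratum size) against a true 11.7. This does not depend on how the overall condition is read. The false-benefit rate under no effect does depend on it: about 7.5% without the condition and about 2% with it (about 15% and 3 to 4% counting either direction).

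The bias reaches the cost per QALY only if the group's own gain is used there. The figures rest on 35% control mortality in every stratum, one two-sided 5% test per stratum, and assumed stratum sizes. The consequence is confined to an exploratory branch of the last secondary endpoint, but the rule is easy to correct before results are known.

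**What to change.** Replace the last sentence of section 10 with:

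*Whenever the overall cost-effectiveness analysis is performed, exploratory results will be reported for all three randomisation strata regardless of significance within a stratum, together with a treatment-by-stratum interaction test on 6-week mortality. Unless that test shows evidence of interaction at a pre-stated level, stratum results will use the overall relative treatment effect applied to stratum-specific baseline mortality and costs.*

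This also settles whether the overall condition applies to the strata. The interaction level has to be filled in before the mortality results are known; the interaction test will itself have low power, which is why the overall relative effect is the default.

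The cost is small. The strata exist and the data are already to be collected, so no visit, procedure or sample size changes. The downside is a little more analysis, and three exploratory results to report instead of only the significant ones.
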